#### 9. DATA ANALYSIS

# 9.1 Power and Sample Size Considerations

To guide enrollment goals, we estimated the sample size required to do a two-sided test with a significance level of 0.05 and a power of 80%. The Food and Drug Administration criteria for demonstrating non-inferiority between IIV and a new vaccine requires comparisons of both the GMR and the SCR. We based expected values for the SCRs and GMRs comparing RIV3 and IIV3 on previously published estimates from prior vaccine immunogenicity trials. We assume that the SCR for IIV4 is  $\geq$ 40% and  $\geq$ 55% for RIV4, based on a clinical trial among adults <65 years demonstrating the SCR for IIV4 to range from 35% to 60% and RIV4 to range from 54%

to 63% against influenza A subtypes (seroconversion rates reported against influenza B viruses reflected trivalent vaccine formulations and were not included).  $^{23,32}$  We intend to have the power to show a 30% relative increase in SCR in the RIV arm compared to the IIV arm. Using the same assumptions and sample size would also provide adequate statistical power to detect a difference in post-vaccination GMT of  $\geq$ 2 fold between study arms if post-vaccination GMT value is  $\geq$ 20 for IIV4 and  $\geq$ 40 for RIV4. **Table 2** provides estimated sample sizes required for varying SCR and differences in SCR between study arms.

Based on prior experience enrolling participants at the two study sites, we will assume that 5% of participants will drop out before study visit 2.

Table 2. Sample size calculations to detect specified differences in SCR between RIV4 and IIV4 at approximately 28 days post-influenza vaccination

SCR at 28 days post- vaccination in IIV arm	Relative increase (%) in SCR in RIV arm compared to IIV arm at 28 days post-vaccination	IV arm Total enrollment for both study arms	
30%	10%	7526	
30%	20%	1926	
30%	30%	874	
40%	10%	4778	
40%	20%	1208	
40%	30%	540	
50%	10%	3130	
50%	20%	776	
50%	30%	340	
60%	10%	2032	
60%	20%	488	
60%	30%	206	

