### 4. STUDY OBJECTIVES

## 4.1 Primary Objective

- Compare humoral immune responses to a single dose of RIV4 versus IIV4 at approximately 28 days after vaccination in the 2019-20 season among HCP ≥ 18 years old who were vaccinated in the 2018-19 season with IIV4 (defined as Group One) as measured by
  - hemagglutination inhibition (HI) titers for egg-grown influenza viruses A/H1N1,
     B/Yamagata, and B/Victoria, and egg-grown and cell-grown A/H3N2
  - o microneutralization (MN) titers for egg-grown and cell-grown A/H3N2 viruses

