#### **6.3.2** Pre-screening and recruitment

The study will be open to HCP meeting the eligibility criteria at the two study sites. Prior to enrollment, study staff will identify potentially eligible HCP from SHIRI enrollment records. Pre-screening procedures may vary by enrollment facility. HCP will be recruited using a combination of methods that will be customized at each study site, including face-to-face meetings, phone calls, and printed material. Each site will describe the methods employed to recruit HCP potentially eligible for enrollment. All potential enrollees will be recorded in a recruitment log (**Appendix A. Recruitment Form**) in order to track invitations, acceptance, and refusal. All HCP who are interested in participation will have a screening and consent

appointment with a study physician, as required in Israel, in order to discuss the study purpose and procedures.

From the start of enrollment, sites will make efforts to recruit HCP from the priority Group One. In parallel HCP from the secondary Group Two will be recruited. If Group One recruitment goals cannot be reached, HCP from the Group One Supplemental will be targeted. A minimum target of 550 participants will be enrolled, including 275 at each site (see Section 9. Data Analysis). The target population of HCP will include 440 HCP from Group One, and 110 HCP from Group Two.

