# Primary Objective

The primary objective of the study is compare humoral antibody responses to IIV4 and RIV4 among Group One HCP as measured by HI (and MN, as appropriate) at baseline (day 0), and approximately 28 days post-vaccination. The proportion of participants that seroconverted (SCR) is defined as  $\geq$  4-fold increase comparing post- versus pre-vaccination titers. Exact 95% confidence intervals will be calculated and the SCR will be compared between vaccine groups using  $\chi^2$  or Fisher exact tests.

Due to the skewed distribution of the resulting titer values, base-2 log transformed titers will be used in analyses and then the summary statistics will be back-transformed to the original scale for presentation of results. The GMT is calculated for each vaccination group as the anti-log2(mean[log2(titeri)]), where *i* represents the titer value for each participant, and 95% confidence intervals assume a normal distribution. To allow for calculation of HI GMTs, a titer of 1:5 will be assigned to those with undetectable HI antibody.

Differences in GMT and GMR will be compared between study groups using separate linear regression models or a generalized linear model that accounted for repeated measures. Odds of achieving elevated post-vaccination titers at seropositive thresholds > 1:40, 1:80, and 1:160 will be compared between study groups by logistic regression.

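### At minimum enrolment, Group One has about 69% power, not 80%, for the 30% relative SCR increase at the plan's 40% control rate, and Table 2 omits the stated 5% dropout

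*Combined protocol and SAP*

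**What the plan says.** Section 9.1 plans for "a two-sided test with a significance level of 0.05 and a power of 80" per cent. It states the aim as "We intend to have the power to show a 30% relative increase in SCR in the RIV arm compared to the IIV arm", and assumes SCRs of at least 40% for IIV4 and at least 55% for RIV4, citing an IIV4 range of 35% to 60%. It adds that "we will assume that 5% of participants will drop out before study visit 2".

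Table 2, whose last column is headed "Total enrollment for both study arms", gives 540 for a 40% control SCR with a 30% relative increase (40% vs 52%). The plan does not say which row sets the sample size.

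Section 6.3.2 sets the recruitment goal: "A minimum target of 550 participants will be enrolled, including 275 at each site (see Section 9. Data Analysis"). It then divides that number: "The target population of HCP will include 440 HCP from Group One, and 110 HCP from Group Two". Section 6.1 gives a range of 550 to 700.

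The primary objective (Section 4.1) concerns HCP "who were vaccinated in the 2018-19 season with IIV4 (defined as Group One"), and Section 9.2 repeats that the aim is to "compare humoral antibody responses to IIV4 and RIV4 among Group One HCP". Group Two serves a secondary objective. Section 6.3.4 randomizes the two groups separately.

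**The concern.** A reader who sets the 540 in Table 2 beside the 550 minimum, which cross-refers to Section 9, will conclude that minimum enrolment delivers 80% power for a 30% increase at a 40% control SCR. Two things stand in the way. The primary comparison uses Group One, so 440 people rather than 550. And the 5% dropout is stated but does not appear to have been applied to the table. No power is given anywhere for the 440.

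If the real power is well below 80%, a non-significant SCR comparison could be taken as evidence against a 30% advantage when the trial had a sizeable chance of missing it.

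**Working it through.** **Inputs.** Two-sided 0.05, 80% power, 30% relative increase, SCR assumptions and 5% dropout (Section 9.1); 440 and 110 (Section 6.3.2); 550 to 700 (Section 6.1); chi-square or Fisher exact test (Section 9.2). Equal arms are assumed unless stated.

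**Step 1: reproduce Table 2.** The pooled-variance formula per arm is

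n = [1.960·√(2·p̄(1−p̄)) + 0.8416·√(p1(1−p1) + p2(1−p2))]² / (p2−p1)².

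For 40% vs 52%, p̄ = 0.46:

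n = [1.960·√0.4968 + 0.8416·√0.4896]² / 0.12² = (1.3815 + 0.5889)² / 0.0144 = 269.6, so 270 per arm and 540 in total.

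This matches, and so do the other 11 rows. None of the 12 contains a dropout allowance. Dividing n per arm by 0.95 and rounding up per arm gives:

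| Control SCR | Increase | Table 2 (reproduced) | With 5% dropout |
|---|---|---|---|
| 30% | 10% | 7526 | 7924 |
| 30% | 20% | 1926 | 2028 |
| 30% | 30% | 874 | 920 |
| 40% | 10% | 4778 | 5030 |
| 40% | 20% | 1208 | 1272 |
| 40% | 30% | 540 | 570 |
| 50% | 10% | 3130 | 3296 |
| 50% | 20% | 776 | 818 |
| 50% | 30% | 340 | 358 |
| 60% | 10% | 2032 | 2140 |
| 60% | 20% | 488 | 514 |
| 60% | 30% | 206 | 218 |

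The printed totals are therefore evaluable numbers. The pair 40% vs 55% is not in the table; the same formula gives 172.8, so 173 per arm, 346 evaluable and 366 enrolled.

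**Step 2: Group One at minimum enrolment.** 440 × 0.95 = 418, or 209 per arm. Power is

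Φ{ [(p2−p1)·√n − 1.960·√(2·p̄(1−p̄))] / √(p1(1−p1) + p2(1−p2)) }.

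- 40% vs 52%: (0.12 × 14.457 − 1.3815) / 0.6997 = 0.505, so 69.3%. Exact enumeration gives 69.9% for chi-square and 66.5% for Fisher.
- 40% vs 55%: (0.15 × 14.457 − 1.3842) / 0.6982 = 1.123, so 86.9%. Exact enumeration gives 86.8% for chi-square and 84.7% for Fisher.

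**Step 3: what 209 per arm can show with 80% power.** Solving the same expression gives either 40% vs about 53.6% (a 34% relative increase), or a 30% increase from a control SCR of about 45.5%. For a 30% increase at other control rates:

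| Control SCR | Power at 418 evaluable |
|---|---|
| 35% | 59.1% |
| 40% | 69.3% |
| 45% | 79.1% |
| 50% | 87.6% |
| 60% | 98.0% |

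**Step 4: other counts, 40% vs 52%.**

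| Who is counted | Evaluable | Power |
|---|---|---|
| All 550, no dropout | 550 | 80.8% |
| All 550, 5% dropout | about 522 | 78.7% |
| Group One, no dropout | 440 | 71.6% |
| Group One, 5% dropout | 418 | 69.3% |
| 700 enrolled, 80/20 split assumed (560 × 0.95) | 532 | 79.5% |
| 700 enrolled, Group Two assumed fixed at 110 (590 × 0.95) | about 560 | 81.5% |

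At the minimum, 80% is reached only by pooling both groups and ignoring dropout.

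Participants vaccinated outside the study join the Vaxigrip arm without randomization (Sections 6.1 and 6.3.4), so the arms may be unequal. As an illustration only, if 88 of the 440 did so, the other 352 would split 176 and 176. The arms would be 264 and 176 enrolled, about 251 and 167 evaluable, and power 67.7%.

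**The case against.** The strongest reply is that the plan assumes 40% vs 55%, a 37.5% relative increase, and for that pair Group One has about 87% power even at the minimum. The plan never says the 30% target applies at exactly 40%; at control rates of 50% or 60%, 418 is ample. This stands and limits the finding. It does not remove it, because 40% is the plan's stated floor, part of the cited 35% to 60% range lies below 45.5%, and the sentence of intent names 30%.

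The plan also names no design row and claims no power for 440, so linking 540 to the 550 minimum is an inference. That is fair. The table's missing dropout allowance does not depend on this inference.

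Enrolment may reach 700, where the 30% target is met or nearly met. That also stands, but 550 is the stated minimum.

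The groups can overlap: Section 6.3.1 allows someone with PCR-confirmed infection also to have been vaccinated in 2018-19. If such people entered the primary analysis, power at the minimum would lie between 69.3% (none of the 110) and 78.7% (all of them), still below 80%. Separate targets and separate randomization point to the lower end.

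Finally, SCR is one of four primary parameters, and Section 9.1 also relies on a 2-fold GMT difference. The documents give no SD; if the log2 SD is assumed to be 1.5 to 2.5, 209 per arm gives about 98% power or more for that difference. The shortfall therefore concerns the SCR target, not the primary objective as a whole.

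**Conclusion.** The concern holds. At the 550 minimum, the intended 80% power for a 30% relative SCR increase is not delivered in Group One if the control SCR is below about 45.5%. At the 40% floor it is about 69%, roughly 11 points short, and it would be 78.7% even if all 550 counted. Table 2 is calculated correctly, but its totals are evaluable numbers under an enrolment heading.

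These figures rest on 5% dropout, equal arms, the uncorrected two-proportion test, and a primary analysis of the 440 only. Under the assumed 40% vs 55%, Group One is adequately powered. This should be fixed, but it is a misstatement of what the minimum can show rather than a flaw in the design.

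**What to change.** Restate Section 9.1 for the primary population. Suggested content: with 440 enrolled in Group One, about 418 evaluable after 5% dropout and equal arms, the trial has 80% power for about a 34% relative increase at a 40% control SCR (40% vs 53.6%), or for a 30% increase when the control SCR is about 45.5% or more; power is about 69% for 40% vs 52% and about 87% for 40% vs 55%. The 30% aim should not stand beside 80% power without that qualification.

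State whether this number includes three kinds of participant:

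- those who meet both group definitions;
- Vaxigrip recipients who were not randomized;
- Group One Supplemental recruits. Section 6.3.1 admits some who were not vaccinated in 2018-19, so they could help fill the 440 without fitting the Section 4.1 population.

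Relabel the last column of Table 2 as evaluable and add the dropout-inflated totals shown above (for the 30% rows: 920, 570, 358 and 218), with a line for 40% vs 55% (346 evaluable, 366 enrolled).

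These are text and table edits. They add no participants and leave the analysis population unchanged; the cost is a less favourable stated power.

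If the team would rather keep 80% power for 40% vs 52%, Group One needs 570 enrolled, 130 more than the minimum (570 − 440). With 110 in Group Two the total is 680, inside the planned 550 to 700.

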# 9.2 Statistical Analysis

HI and MN results will be measured by four primary parameters: SCR, post-vaccination GMT ratio, GMR, and post-vaccination titers equal or greater than seropositive thresholds at 1:40, 1:80, and 1:160. SCR will be defined as the proportion of participants with paired samples that achieved ≥ 4 fold rise comparing post vs pre-vaccination titers and post vaccination titers ≥ 1:40. GMR will be defined as the mean of the ratio of post-vaccination HI/MN titer and pre-vaccination HI/MN titer for each subject.

# Primary Objective

The primary objective of the study is compare humoral antibody responses to IIV4 and RIV4 among Group One HCP as measured by HI (and MN, as appropriate) at baseline (day 0), and approximately 28 days post-vaccination. The proportion of participants that seroconverted (SCR) is defined as  $\geq$  4-fold increase comparing post- versus pre-vaccination titers. Exact 95% confidence intervals will be calculated and the SCR will be compared between vaccine groups using  $\chi^2$  or Fisher exact tests.

Due to the skewed distribution of the resulting titer values, base-2 log transformed titers will be used in analyses and then the summary statistics will be back-transformed to the original scale for presentation of results. The GMT is calculated for each vaccination group as the anti-log2(mean[log2(titeri)]), where *i* represents the titer value for each participant, and 95% confidence intervals assume a normal distribution. To allow for calculation of HI GMTs, a titer of 1:5 will be assigned to those with undetectable HI antibody.

Differences in GMT and GMR will be compared between study groups using separate linear regression models or a generalized linear model that accounted for repeated measures. Odds of achieving elevated post-vaccination titers at seropositive thresholds > 1:40, 1:80, and 1:160 will be compared between study groups by logistic regression.

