#### 6.3.4 Randomization

Using the list of HCP consented to participate in the study, HCP will be randomized 1:1 to receive one 0.5 mL intramuscular dose of Flublok® Quadrivalent or Vaxigrip Quadrivalent. Randomization lists will be generated by the epidemiologist and data analyst using block randomization to ensure equal sample size in each group.

Randomization will be conducted after enrollment is completed. Randomization will occur separately for participants in Group One and Group Two.

Randomization will not occur for enrolled participants who were vaccinated with Vaxigrip outside of the study.

# 6.4 Study visit 1

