### 6.4.1 Pre-vaccination Questionnaire

All study participants, except those who were already vaccinated outside of the study, will complete a second brief questionnaire to determine whether they are currently experiencing fever, decreased energy, muscle aches, headache, or nausea, and will be asked to rate the subjective severity of any symptom(s) as mild, moderate, or severe (Appendix E. Prevaccination Questionnaire/Vaccine Administration Form). Appendix E will also readdress the study exclusion criteria. Participants reporting subjective fever (of any severity) and those reporting no fever but one or more symptom of moderate or severe subjective severity will not receive study vaccine until their illness has resolved. In this case, a follow up appointment will be made after resolution of the illness, at which time the participant will receive the vaccine. Study number assignment and pre-vaccination blood draw will take place on the day of vaccine administration.

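### Section 9.2 leaves the day-0 titre out of the SCR test and the titre-threshold models: efficiency forgone, by an amount the documents do not fix, that one prespecified covariate could recover

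*Combined protocol and SAP*

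**What the plan says.** Section 9.1 sizes the trial on SCR: "we estimated the sample size required to do a two-sided test with a significance level of 0.05 and a power of 80" per cent, and "We intend to have the power to show a 30% relative increase in SCR in the RIV arm compared to the IIV arm". The control value is given as "We assume that the SCR for IIV4 is" at least 40%.

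Section 9.2, Primary Objective, fixes the analysis of the two kinds of binary parameter. For SCR: "Exact 95% confidence intervals will be calculated and the SCR will be compared between vaccine groups using" χ² or Fisher exact tests. The odds of a titre above 1:40, 1:80 or 1:160 "will be compared between study groups by logistic regression", with no covariate named.

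The one statement about adjustment is under Secondary Objectives in 9.2. It assumes that randomisation deals with confounding and leaves models unadjusted unless univariate analysis shows that the arms differ.

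The baseline value is available. Section 6.4.1 says that the "pre-vaccination blood draw will take place on the day of vaccine administration", and the Project Summary confirms a pre-vaccination sample for all randomised participants. Participants vaccinated with Vaxigrip outside the study have no day-0 sample. Section 6.4.2 uses their SHIRI sample from the end of the 2018-19 season instead.

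**The concern.** Group One was vaccinated the season before, so day-0 titres are likely to vary widely and to predict both kinds of outcome. A high starting titre makes a 4-fold rise harder. A participant already at 1:40 before vaccination will usually be at 1:40 afterwards, whichever vaccine was given. A two-by-two test leaves that predictable variation in the error term, as does a logistic model with study group alone.

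What is at stake is precision, not bias: randomisation protects the unadjusted comparison. The imbalance-triggered rule is a weak substitute. It makes adjustment depend on the data, and it forgoes the gain whenever the arms happen to be balanced, although a prognostic covariate improves precision then too.

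**Working it through.** **1. The plan's own figure.** Inputs from 9.1 and 6.3.4: two-sided 0.05, 80% power, 1:1 allocation, p0 = 0.40, p1 = 0.40 × 1.30 = 0.52, mean p = 0.46.

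n per arm = [1.96·√(2·0.46·0.54) + 0.8416·√(0.40·0.60 + 0.52·0.48)]² / 0.12² = [1.96·0.7048 + 0.8416·0.6997]² / 0.0144 = 269.6, rounded up to 270, so 540 in total.

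This matches Table 2, and the same formula reproduces all twelve rows. Table 2 is therefore sized for the unadjusted test, without dropout inflation.

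**2. Unadjusted power in the primary population.** The Group One target is 440 (section 6.3.2). Less 5% dropout, that is 418, or 209 per arm.

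Power = Φ[(0.12·√209 − 1.96·0.7048)/0.6997] = Φ(0.505) = 69.3%.

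**3. Effect of a baseline covariate, by approximation.** If day-0 log2 titre correlates r with the binary outcome within arm, adjustment acts like an effective sample size of n/(1 − r²). The documents give no r, so it is varied.

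| Absolute r (assumed) | Effective n from 209 per arm | Power, 209 per arm | Power, 270 per arm |
|---|---|---|---|
| 0 | 209 | 69.3% | 80.1% |
| 0.2 | 217.7 | 71.1% | 81.6% |
| 0.3 | 229.7 | 73.4% | 83.6% |
| 0.4 | 248.8 | 76.8% | 86.4% |
| 0.5 | 278.7 | 81.3% | 90.0% |

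**4. Simulation.** Two-fold dilution titres with a floor of 1:5 were simulated at 209 per arm. SCR was set to 40% versus 52%; for a titre of at least 1:40, rates of 75% versus 85% were assumed. The assumed log2 SD was 1.5 to 2.0, day-0 GMT 20 or 40, and pre/post correlation 0.3 to 0.8. Monte Carlo error is about 1 point. SCR was run under both definitions in the plan: the 4-fold rise alone (5.1 and 9.2, Primary Objective), and the 4-fold rise plus a post-vaccination titre of at least 1:40 (opening of 9.2).

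Results for SD 1.5 and day-0 GMT 40, unadjusted to adjusted power (gains taken before rounding):

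| Pre/post correlation | SCR, 4-fold only, linear term | SCR, 4-fold and at least 1:40, quadratic term | Titre at least 1:40, linear term |
|---|---|---|---|
| 0.3 | 69.0 to 79.2 (+10.2) | 68.6 to 76.3 (+7.8) | 75.5 to 76.0 (+0.5) |
| 0.5 | 70.1 to 76.9 (+6.8) | 70.1 to 74.6 (+4.5) | 70.6 to 75.6 (+5.0) |
| 0.7 | 71.2 to 74.6 (+3.4) | 71.4 to 73.4 (+2.1) | 73.2 to 86.0 (+12.8) |
| 0.8 | 71.4 to 73.4 (+2.0) | 69.8 to 70.9 (+1.1) | 76.3 to 90.6 (+14.3) |

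Over all scenarios in this set:
- SCR, 4-fold only: −0.3 to +10.2 points.
- SCR with the 1:40 requirement: about −1 to +6.5 with a linear baseline term, +0.4 to +7.8 with a quadratic term.
- Titre at least 1:40: +0.5 to +15.4.

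Further simulations, with day-0 GMT about 20 to 57 and pre/post correlation 0.3 to 0.7, gave about 1 to 12 points for SCR and 0 to 20 for the thresholds, with no loss beyond Monte Carlo error. In a run of the baseline-standardised difference, type I error was similar for the two analyses (all values between 4.2% and 6.3%).

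**5. Pattern.** SCR gains most when pre and post titres correlate weakly; the thresholds gain most when they correlate strongly. Under the stricter SCR definition the dependence on baseline is not monotone: from 1:5 a 4-fold rise reaches only 1:20, so an 8-fold rise is needed. That is why a linear term can do nothing there and a curved term does better.

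**The case against.** The case against has several parts, and most of it limits the point rather than removing it.

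- **No planned power is lost.** The 80% at 540 was computed for the unadjusted test, so design and analysis agree. This stands. A reader might infer that the χ² test leaves the trial short of its stated power; the documents do not support that.
- **The 69% is not caused by the test.** It comes from setting 440 Group One participants less 5% against a table entry of 540, which is a separate sample-size matter. Section 9.1 also assumes at least 55% for RIV4. At 40% versus 55% the unadjusted power with 209 per arm is 86.9%. Section 6.1 allows enrolment up to 700. All of this stands.
- **The gain cannot be derived from the documents.** They give no titre SD, day-0 distribution, threshold rates or baseline-outcome correlation. A reader might infer one double-digit loss common to all the binary endpoints. That is unsupported: SCR is already a ratio to the day-0 titre, and in many scenarios it gained under 3 points.
- **The plan does not forbid baseline adjustment in the threshold models.** It is silent there, and the imbalance rule sits under Secondary Objectives. This stands; the defect is missing prespecification.
- **Other primary parameters already use baseline.** GMR does, so a missed RIV4 advantage on SCR or a threshold would not be missed on every parameter. This stands.
- **Not everyone has a day-0 titre.** Section 6.1 places those vaccinated outside the study in the Vaxigrip arm with a SHIRI baseline. Restricting the model to randomised participants leaves them out, and the plan must say so.

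None of this shows a cost to adjusting randomised participants for a value already measured.

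**Conclusion.** The point holds as forgone efficiency. The SCR comparison that sizes the trial takes no covariate, the threshold models specify none, and the one adjustment rule is driven by the data, while every randomised participant is bled on the day of vaccination.

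The size is conditional. At 209 per arm and 40% versus 52%, the gain is about 2 points at an absolute r of 0.2 and about 12 at 0.5. Across the simulated scenarios it is roughly 0 to 12 points for SCR and 0 to 20 for the thresholds. Linked SHIRI titres (section 6.7) could narrow these ranges before analysis.

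Adjustment does not replace settling the Group One sample size. Bringing 209 per arm up to the equivalent of 270 would need r² = 1 − 209/270 = 0.226, an absolute r of 0.48, and the largest value for SCR in the first set of simulations (step 4) was 0.46. The change is worth making, but the plan is not invalid without it.

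**What to change.** In section 9.2, Primary Objective:

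1. Prespecify, as the main comparison for SCR and for each titre threshold, a logistic model with study arm and log2 day-0 titre for the same strain, assay and substrate. If the SCR definition that also requires a titre of at least 1:40 is kept, give baseline a quadratic or spline term in the SCR model.
2. Report the baseline-standardised proportion in each arm and their difference with a 95% CI. This keeps the comparison on the SCR-difference scale and avoids relying on an odds ratio conditional on baseline.
3. Keep the unadjusted proportions with exact CIs and the χ² or Fisher test as supporting output, and as the fallback where cells are too sparse to fit the model.
4. Apply the model to randomised participants with a day-0 sample. State that participants vaccinated outside the study, who have only an end-of-season SHIRI sample, are not in this adjusted comparison.
5. State that this adjustment is made whether or not the arms differ at baseline.

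The cost is a few sentences and one model term (two or more if the baseline effect is curved). No new data are needed, and no randomised participant with paired samples is dropped.
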